PHASE 1: - \$25/person x2 visits = \$100 - Parking \$13/family per visit (x2 visits) = \$26 - For those agreeing to beta-test the app: Data use: \$10 - For those agreeing to participate in filming the video to be used in the app: \$50 - Max compensation/family = \$186

Providers will not receive financial incentives, but will be recognized in scholarly works from this study.

PHASE 2: - \$25/person x2 visits = \$100 - Parking \$13/family per visit (x2 visits) = \$26 - \$5/visit for bringing all actively used glucometers to each visit (2 visits)= \$10 - Bi-Weekly rating \$5/person (2 people, up to 8*ratings) = \$80 - Data Use: \$10/mo of app use (up to 4*months) = \$40 - Max compensation/family = \$256

All participants in both phases: small (<\$2 in value) gift item (silicone adhesive cell phone wallet) branded with the study logo for participant retention

A ClinCard will be used for reimbursement, unless it is not available, in which case, cash or check will be used.

Section M: Genetics

How would you classify your genetic study?

Discuss the potential for psychological, social, and/or physical harm subsequent to participation in this research. Please discuss, considering the following areas: risks to privacy, confidentiality, insurability, employability, immigration status, paternity status, educational opportunities, or social stigma.

Will subjects be offered any type of genetic education or counseling, and if so, who will provide the education or counseling and under what conditions will it be

provided? If there is the possibility that a family's pedigree will be presented or published, please describe how you will protect family member's confidentiality?

Section N: Sample Collection

None

Section O: Drug Studies

Does the research involve the use of ANY drug* or biologic? (*A drug is defined as any substance that is used to elicit a pharmacologic or physiologic response whether it is for treatment or diagnostic purposes)

No

Does the research involve the use of ANY gene transfer agent for human gene transfer research?

No

O1. Current Drugs

Is this study placebo-controlled?

No

Will the research involve a radioactive drug?

No

Section P: Device Studies

Does this research study involve the use of ANY device?

No

Section Q. Consent Form(s)

None

Section R: Advertisements

None

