Phase 2: A two-group randomized design will be used to conduct the pilot intervention trial with n=82 adolescent-parent dyads. Participating families will be enrolled and randomized 2:1 to Group A-Intervention or B-Control (A=54, B=28). During the 3-month period, group A will receive the intervention while B serves as the control and receives usual care. Data collection will occur at baseline and approx 3 months (the 2nd data collection will occur at the subsequent diabetes clinic visit, which usually occur approximately every 3-4 months)

Inclusion Criteria:

Families will be eligible for both phases of the study if: 1) adolescent is between the ages of 12-17 years at enrollment; 2) receives treatment for T1D at Texas Children's Hospital (TCH); 3) T1D diagnosis of at least 6 months; 4) parent and adolescent exhibit fluency in reading/speaking English; & 5) parent has mobile device with a data plan.

Providers will be eligible for phase 1 if he/she: 1) provides treatment to adolescents (12 - 17 years old) with T1D, & 2) provides T1D treatment at one of the TCH diabetes clinics.

Exclusion Criteria:

Families will be excluded from both phases of the study if there is a serious medical, cognitive, or mental health comorbidity in parent or adolescent that would preclude ability to provide informed consent or participate in data collection or intervention. Families will be excluded from Phase 2 if they participated in Phase 1 or if they have participated in another intervention study in the previous 6 months prior to enrollment.

Providers will be excluded from Phase 1 if he/she is primarily a researcher or only providing treatment to non-T1D patients.

F2. Procedure

The study will be conducted in two phases.

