- Glycemic control measured by glycosylated hemoglobin A1c will be extracted from the medical record. A1c values are obtained in the course of routine clinical care in the TCH diabetes clinics.

(3) Intervention Process Measure (Study staff will collect ratings biweekly via email, telephone, or text message, during Phase 2)

- Parents and adolescents will each rate their relationship quality in relation to diabetes management using 3 items adapted from the Parent-Youth Relationship Index of the National Longitudinal Study of Youth-1997.

(4) Intervention Satisfaction and Feedback (Study staff will collect data for these measures following the intervention periods in both phases. - - Participants will complete the USE Questionnaire, a 32-item measure of the users' perceived usefulness of, satisfaction with, and ease of use of a particular technology.

- Semi-structured interviews with parents and adolescents in the intervention group will be conducted to contextualize survey responses, discuss user perspectives on the app (e.g., intrusiveness of prompts, clarity/relevance of response options, usefulness and appeal of strength behavior feedback charts), and obtain suggestions for improvement. The interviews will be conducted in person (in private meeting space) or over the telephone, whichever is most convenient for the family. The qualitative interviews will be audio-recorded and transcribed verbatim by medical transcriptionists for qualitative coding and analysis. The responses will inform future expansion of this study.

Section G: Sample Size/Data Analysis

G1. Sample Size

How many subjects (or specimens, or charts) will be used in this study?

Local: 112 Worldwide: 112

Please indicate why you chose the sample size proposed:

The purpose of this study is to develop and evaluate the feasibility of a strengths-based behavioral mHealth intervention for parents of adolescents with T1D, delivered via a smartphone app. In order to adequately capture the variability of experiences and preferences among adolescents with diabetes and their families, we propose to enroll a total of 97 participants, in the following way:

PHASE 1: 10 adolescent-parent dyads, 5 diabetes care providers PHASE 2: 82 adolescent-parent dyads

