This sample size should be sufficiently large to conduct the qualitative and quantitative analyses to address the study aims and research questions. To allow for possible attrition or other loss of enrolled participants, we have added an additional 15% to our sample size estimate: $97 + 15 = 112$

G2. Data Analysis

Provide a description of your plan for data analysis. State the types of comparisons you plan (e.g. comparison of means, comparison of proportions, regressions, analysis of variance). Which is the PRIMARY comparison/analysis? How will the analyses proposed relate to the primary purposes of your study?

Qualitative Data (PHASES 1 and 2): Audio recordings will be transcribed verbatim by a medical transcription company and errors will be corrected prior to analysis. Thematic analysis will be used to analyze the qualitative data. Two coders will independently code and analyze the transcripts, and will discuss discrepancies to reach a joint coding resolution. The research team will meet throughout the coding and analysis process to discuss emerging themes and patterns. To protect confidentiality, transcripts will be coded by participant number not names.

Quantitative Data (PHASE 2) : Intervention feasibility will be determined if the upper bound of the 95% exact, binomial confidence interval (CI) is greater than or equal to 95% for downloading the app and greater than or equal to 70% for using the app at least twice per week. Acceptability will be measured as the proportion of participants who rate the intervention as acceptable (somewhat to very much) with 95% exact, binomial CIs (upper bound should be greater than or equal to 80%).

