The primary analysis of glycemic and behavioral outcomes will be to compare the change in response (V1 vs. V2) between groups using an independent, two-sample t-test. Equal variances will be assumed, unless the F test rejects the null hypothesis of equality. Quantile-quantile plots, stratified by group, will be used to test for approximate normality, and data transformations (e.g., natural logarithm) will be used if needed. All outcome measures will be independently compared between groups, and no adjustments for multiple hypothesis tests will be made in this pilot study. A general linear mixed model will also be used to compare groups and will allow for the use of all available data, including incomplete observations. The model will assume an unstructured matrix of correlated error terms to account for repeated observations. Statistical significance will be assessed at the 0.05 level for all hypothesis tests. A total sample size of $n=82$ with complete data would be required to detect an effect size of 0.75 with 80% power using an independent, two-sample t-test assuming $\alpha=0.05$. This sample size will also have >95% probability of generating binomial confidence intervals with half-widths ≤ 0.20 . Therefore, this study will plan to enroll $n=82$ (54 intervention, 28 control) in the pilot intervention trial (Phase 2) to allow for a 20% attrition rate.

Data from the second intervention period (V2) will be exploratory. A similar analysis will be used including independent, two-sample t-tests and general linear mixed models. Maintenance or drop-off of intervention engagement past three months will be observed for group A. Descriptive analyses of pre-post outcomes for both groups during the 3-month study period (V1-V2) will maximize this pilot sample's data to estimate trends and receive additional qualitative feedback.

Section H: Potential Risks/Discomforts

H1. Potential Risks/Discomforts

Describe and assess any potential risks/discomforts; (physical, psychological, social, legal, or other) and assess the likelihood and seriousness of such risks:

The risks associated with this study are relatively minor, as the protocol does not involve any medical procedures and the study procedures and intervention do not include any treatment or advice related to medical care of diabetes or treatment of psychological conditions. No study procedures or questions will

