The purpose of the proposed study is to develop and evaluate the feasibility, acceptability, and initial impact of a pilot behavioral mobile health (mHealth) intervention for parents of adolescents with type 1 diabetes. Based on participant input and feedback in the first phase of the study, qualitative phase of the study, the intervention will use a smartphone app to teach parents strategies to identify and reinforce strength behaviors their adolescents engage in related to diabetes management, and will prompt parents to monitor and reinforce these behaviors throughout the day. Supportive parent involvement in adolescents' diabetes management is known to improve family relationships, treatment adherence, quality of life, and glycemic control, and therefore it is hypothesized that adolescents and parents in this study will experience similar benefits. Participants in Phase 1 of the study may enjoy the process of contributing to developing a research intervention and having their input heard. In the Phase 2, parents may benefit from learning strengths-based parenting strategies, and adolescents may appreciate having their positive behavior recognized.

Diabetes care providers who participate in Phase 1 will have the opportunity to be recognized in or contribute to academic works resulting from this research after the study has been completed.

Describe potential benefit(s) to society of the planned work.

Behavioral interventions have demonstrated an impact on family relationships related to diabetes management, quality of life, adherence, and glycemic control, however for many youth and families, daily management demands remain a struggle and glycemic control remains suboptimal. The proposed study aims to evaluate whether a novel behavioral intervention, designed in collaboration with families and delivered via an engaging, inexpensive, and low-burden smartphone app, can enhance these important outcomes and promote resilience in adolescents with type 1 diabetes. The results will optimally lead to dissemination of a useful and engaging intervention for families of adolescents and will inform future behavioral mHealth interventions for this population.

Do anticipated benefits outweigh potential risks? Discuss the risk-to-benefit ratio.

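### Feasibility and acceptability pass when the upper exact 95% confidence limit reaches the target, so 48/54 downloads (89%) and 31/54 regular users (57%) meet targets of 95% and 70%

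*Combined protocol and SAP*

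**What the plan says.** Section D gives the purpose as developing the app intervention and evaluating its feasibility. Section I (Potential Benefits) widens this to "evaluate the feasibility, acceptability, and initial impact of a pilot behavioral mobile health (mHealth) intervention".

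The decision rule is in Section G2, under quantitative data for Phase 2:

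- Download: "Intervention feasibility will be determined if the upper bound of the 95% exact, binomial confidence interval (CI) is greater than or equal to 95" percent.
- Use: the same upper bound must be "greater than or equal to 70% for using the app at least twice per week".
- Acceptability: the proportion rating the intervention acceptable is given with an exact interval, and the "upper bound should be greater than or equal to 80" percent.

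No section adds a condition on the observed proportion or on the lower limit. Section F1 puts 54 dyads in the intervention group. Section G2 sizes the trial "to allow for a 20% attrition rate". Section F2, Assessments (4), says "Participants will complete the USE Questionnaire", and parents and adolescents are both interviewed. G2 does not say whose rating counts for acceptability.

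**The concern.** An exact 95% interval holds the rates that the data are compatible with. If its upper end reaches the target, the data have failed to show that the rate is below target. That is not evidence that the rate is at target, yet the plan says feasibility is then determined.

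The rule also rewards imprecision. The fewer the dyads, the wider the interval and the easier it is to pass.

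What is at stake is the pilot's main conclusion. It could be reported as feasible and acceptable on rates well short of the plan's own targets. Section I expresses the hope that "The results will optimally lead to dissemination of a useful and engaging intervention for families of adolescents", so a favourable label may be relied on in later work.

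**Working it through.** **Inputs.** Targets of 95%, 70% and 80% (G2). Intervention group n = 54 (F1, F2, G2). Attrition of 20% (G2): 0.80 × 54 = 43.2, taken as 43. The plan does not state the denominators, the rating unit, or how twice-weekly use is summarised over about three months. I assume all 54 dyads and one acceptability rating per dyad unless stated otherwise.

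**Formula.** For x successes in n, the exact (Clopper-Pearson) 95% limits are

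- lower = the 0.025 quantile of Beta(x, n − x + 1)
- upper = the 0.975 quantile of Beta(x + 1, n − x)

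**The plan's own precision figure.** G2 claims better than 95% probability of half-widths no larger than 0.20. Over all possible counts, the largest half-width is 0.139 at n = 54 and 0.156 at n = 43. The claim reproduces, so the interval method is being read as the plan intends.

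**Lowest passing counts at n = 54.**

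| Criterion | Target | Lowest pass | Upper limit | One fewer | Shortfall |
|---|---|---|---|---|---|
| Download | 95% | 48/54 = 88.9% | 95.8% | 47/54: 94.6%, fails | 6.1 points |
| Use twice weekly | 70% | 31/54 = 57.4% | 70.8% | 30/54: 69.1%, fails | 12.6 points |
| Acceptability | 80% | 37/54 = 68.5% | 80.5% | 36/54: 78.9%, fails | 11.5 points |

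**Other denominators.** At n = 43 the lowest passes are 38 (88.4%), 24 (55.8%) and 29 (67.4%). If parent and adolescent ratings are pooled (n = 108), acceptability passes at 78/108 = 72.2% (upper limit 80.4%).

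**Effect of sample size.** The lowest passing download rate is 17/20 (85%) at n = 20, 48/54 (89%) at n = 54 and 184/200 (92%) at n = 200.

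**Chance of passing each criterion**, P(X ≥ c) with X ~ Bin(54, p) and c = 48, 31 and 37:

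| Criterion | On target | Below target | Further below | Furthest below |
|---|---|---|---|---|
| Download | 95%: 98% | 90%: 71% | 85%: 28% | 80%: 6.5% |
| Use | 70%: 98% | 60%: 70% | 55%: 42% | 50%: 17% |
| Acceptability | 80%: 99% | 70%: 66% | 65%: 35% | 60%: 13% |

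If 108 pooled ratings are treated as independent, acceptability passes with probability 35% at a true 70% and 78% at a true 75%. The corresponding figures with 54 ratings are 66% and 89%.

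**Feasibility as a whole (download and use).** A user must first have downloaded the app, so

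P = Σ over d ≥ 48 of Bin(d; 54, p_D) × P(Bin(d, p_U / p_D) ≥ 31)

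- At p_D = 0.90 and p_U = 0.60: 0.551 (0.497 if the two were independent).
- At 0.85 and 0.55: 0.18.
- At 0.80 and 0.50: 0.03.
- On target, at 0.95 and 0.70: 0.967.

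**The case against.** The strongest defence is that the rule is a deliberately lenient screen for a minimal-risk pilot: do not call the intervention infeasible unless the data exclude the target. Several facts support this reading.

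- The upper bound appears in two separate sentences, so a slip is unlikely.
- A lower-limit rule at the same download target could never be met, because 54/54 has a lower limit of only 93.4%.
- The rule does discriminate further from target, as the tables show.
- There is no formal progression rule, and nothing ties dissemination to passing.
- The acceptability estimate and its interval are planned output, so readers would see a shortfall.

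These facts are correct, and they limit the harm to the label attached to the result: the estimates themselves are not biased. But the wording does not describe a screen for excluding infeasibility. It says feasibility is determined when the condition holds. Being a pilot does not excuse this, because feasibility is what the pilot is for. Leniency can be had openly through lower targets.

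A second objection is that a point-estimate rule is harsh on an intervention exactly on target. That is true, and the cost is set out with the fix.

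**Conclusion.** The concern holds. As written, all three criteria equate not excluding the target with reaching it. Observed rates 6 to 13 points below target pass. At true rates of 90% for download and 60% for use, feasibility is declared with probability of about 55%.

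The sizes assume 54 dyads, complete data, one acceptability rating per dyad and users as a subset of downloaders. The direction does not depend on these assumptions: it is the same at 43 dyads and with 108 pooled ratings. Attrition is not the cause, since a 20% loss moves the acceptability cut-off only from 68.5% to 67.4%. Because this is the decision rule for the pilot's stated purpose, it should be corrected before results are seen.

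**What to change.** Declare each criterion met only if the observed proportion reaches its target, and report the exact 95% interval as a statement of precision.

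- **Download and use:** use all randomised Group A dyads as the denominator, counting non-downloaders and non-users as failures. The cut-offs are 52/54 (0.95 × 54 = 51.3) and 38/54 (0.70 × 54 = 37.8).
- **Acceptability:** use those who give a rating. The cut-offs are 44/54 if all rate (0.80 × 54 = 43.2) and 35/43 at 20% loss (0.80 × 43 = 34.4). Report the number not rating. Count non-raters as failures only in a sensitivity analysis, because 43 raters could reach at most 43/54 = 79.6%.
- **Rating unit:** state in advance whether it is the parent, the adolescent or one rating per dyad.

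**What it gains.** The pass chance falls to 8% at true download 90%, 8% at true use 60%, and 7% at true acceptability 70% (43 raters; 4% with 54). Joint feasibility at 90% and 60% falls from 55% to 2%.

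**What it costs.** A few sentences of wording, with no extra data or participants, but stricter criteria. At true rates exactly on target, the pass chance falls from about 98% per criterion to 49% (download), 54% (use) and 50% (acceptability, 43 raters). Joint feasibility falls from 97% to 32%. All three together, treated as independent with 43 raters, fall from about 95% to about 13%. On the same basis, all three pass with probability of about 52% at true rates of 97%, 75% and 85%, and about 86% at 98%, 80% and 90%.

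If that is too strict, openly lower targets with a lower-limit rule, or graded zones, are reasonable alternatives. The point-estimate rule is the smallest change that keeps the plan's targets.

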(PHASE 2) For Phase 2, study staff will review upcoming scheduled appointments in the diabetes care center, and will screen the electronic medical records of scheduled patients for inclusion and exclusion criteria. Potentially eligible families will be sent an informational letter about the study, including instructions to contact study staff to learn more about the study or to opt-out of being contacted about the study. For families who do not opt-out, study staff will meet with them at the next scheduled diabetes clinic visit to confirm eligibility, describe the study protocol and risks in detail, and answer questions. Families who meet eligibility requirements and agree to participate will sign all required informed consent and assent forms and will receive a copy of the signed forms for their records.

During Phase 2, following consent and enrollment at the baseline clinic visit (V1), 82 adolescent-parent dyads will individually complete a questionnaire battery and will provide blood glucose meter for the staff to download data. They will also provide consent for study staff to review the patient's medical chart to document birth date, date of diagnosis, current insulin regimen, diabetes-related ER visits or hospitalizations, and most recent hemoglobin A1C - for the next 12 months.

Families will then be randomized using a 2:1 ratio to Group A or B (A=54, B=28). Group A will begin the intervention immediately. Research staff will provide verbal and written instruction on how to install and use the mobile phone app and will instruct families to begin using the app that day. Group B will be the control group for the entirety of the study and will receive usual care. At the V2 clinic visit (approx. month 3, or at the time of the next diabetes clinic visit), participants in Group A will stop using the app, and both groups will complete the questionnaire battery/provide meter for download again. At this time, Group A will provide qualitative feedback about their experiences and recommendations to improve the intervention. To assess the process of the intervention's impact, adolescents and parents in both groups will each provide biweekly ratings (via email, text message, or telephone) of their parent-adolescent relationship quality throughout the full study period (V1-V2).

Incentives will be distributed to participants following completion of each time point, as outlined in section L.

ASSESSMENTS:

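### The primary change-score t-test fixes the baseline slope at 1; if the slope is common to both arms, adjusting for V1 can tighten the comparison at small cost

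*Combined protocol and SAP*

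**What the plan says.** Section G2 (Data Analysis) states that the primary analysis of the glycemic and behavioral outcomes will "compare the change in response (V1 vs. V2) between groups using an independent, two-sample t-test". On variances it says: "Equal variances will be assumed, unless the F test rejects the null hypothesis of equality". A second analysis is added: "A general linear mixed model will also be used to compare groups and will allow for the use of all available data, including incomplete observations". Its errors are to be unstructured, but its fixed effects are not listed. No section names a baseline covariate.

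Section G2 also says "Statistical significance will be assessed at the 0.05 level for all hypothesis tests", and that n=82 "with complete data would be required to detect an effect size of 0.75 with 80% power using an independent, two-sample t-test". It then says that enrolling 82 allows for 20% attrition.

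Section F2 (Phase 2) gives the order of events. First, "following consent and enrollment at the baseline clinic visit (V1), 82 adolescent-parent dyads will individually complete a questionnaire battery" and hand over the glucose meter for download. Allocation to Groups A and B (2:1, 54 and 28) comes after that. A1c is handled differently: "Glycemic control measured by glycosylated hemoglobin A1c will be extracted from the medical record", from values obtained in routine care.

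**The concern.** A t-test on V2 minus V1 uses the baseline, but forces its coefficient to be exactly 1. When the true slope of V2 on V1 is below 1, subtracting all of V1 over-corrects and adds noise. Estimating the slope, by ANCOVA or an equivalent mixed model, removes that noise. V1 is measured before allocation, so it is a legitimate covariate and needs no new data.

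About 66 dyads are expected to have both visits, and the plan powers and tests these outcomes at the 0.05 level. Unnecessary width in each interval therefore matters. The planned mixed model does not settle the question as written. With free group-by-visit means and complete data it returns the same contrast as the change score. With one common V1 mean it acts as a baseline-adjusted analysis. The plan does not say which is meant.

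**Working it through.** **Inputs.** From Section G2: effect size 0.75, 80% power, level 0.05 (taken as two-sided, since sidedness is not stated), 20% attrition. From Section F2: 54:28. Completers: 82 × 0.8 = 65.6, taken as 66 (44:22). Assumed, because the documents do not give them: the V1-V2 correlation rho, and the SD ratio k = SD2/SD1.

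**Reproducing the plan's figure.** With a noncentral t and 0.75 in units of the SD of change, power is 80.4% at 43:22 and 80.8% at 44:22. Since 66/0.8 = 82.5, the 82 reproduces as the number enrolled. With all 82 complete (54:28), power would be 88.9%.

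**Variance ratio.** Set SD1 = 1 and assume one slope, b = rho × k, in both arms.

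- Change score: variance is proportional to k²(1 − rho²) + (1 − b)².
- ANCOVA: variance is proportional to k²(1 − rho²) × [1 + 1/(N − 4)]. The bracket is the cost of estimating the slope: 1 + 1/62 = 1.0161 at N = 66, or 1 + 1/78 = 1.0128 if all 82 are complete.
- Ratio: k²(1 − rho²) / (1 + k² − 2·rho·k) × 1.0161. At k = 1 this is (1 + rho)/2 × 1.0161.

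| rho | ratio, k = 0.8 | ratio, k = 1 | ratio, k = 1.25 | ANCOVA power, k = 1 |
|---|---|---|---|---|
| 0.5 | 0.581 | 0.762 | 0.907 | 90.0% |
| 0.7 | 0.638 | 0.864 | 0.997 | 86.1% |
| 0.8 | 0.650 | 0.915 | 1.016 | 84.1% |
| 0.9 | 0.618 | 0.965 | 0.965 | 82.1% |

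**Power at k = 1.** The change score has noncentrality 0.75/√(1/44 + 1/22) = 2.872 on 64 df, giving 80.8%. ANCOVA has 2.872/√ratio on 63 df: 3.290, 3.090 and 2.923 at rho 0.5, 0.7 and 0.9. The 95% half-width falls from 0.522 to 0.456, 0.485 and 0.513 change-SD units. Simulation agrees with these variance ratios.

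**Where adjustment loses, common slope.** The loss peaks at b = 1 (for example rho 0.8 with k = 1.25): 1.6% more variance and power of 80.1%. With equal SDs, break-even is rho = 2/1.0161 − 1 = 0.968.

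**Unequal slopes (A, B), by simulation.** Pooled-slope ANCOVA gives ratios of about 0.85 at (0.5, 0.7), 0.96 at (0.5, 0.9) and 0.87 at (0.9, 0.5). It loses at some pairs: 1.05-1.06 at (0.7, 1.1) and 1.07-1.08 at (0.6, 1.2).

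**Unequal residual variance, by simulation.** With residual SD 0.7 in A and 1.0 in B, type I error is 6.1% for the planned F-test-then-t-test, 7.9% for pooled-variance ANCOVA and 4.8% for ANCOVA with HC3 standard errors. Using HC3 always has a price: 88.7%, 84.5% and 80.4% power at rho 0.5, 0.7 and 0.9 with equal SDs. Near slope 1 (rho 0.8, k = 1.25) it gives 78.8%, against about 81% for the planned test.

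**Attrition, by simulation** (54:28, 20% loss, equal SDs). Suppose loss depends on baseline in Group A only, with log-odds 1 per SD. The complete-case change score is then biased by 0.087, 0.051 and about 0.018 outcome SD at rho 0.5, 0.7 and 0.9. A mixed model with group, visit and their interaction has bias of about 0.001 or less, even with separate V1 means. If loss depends on baseline equally in both arms, the change-score bias is at most 0.0002.

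**The case against.** The strongest objection is that nothing is wrong. Section F1 labels the study a pilot, its purpose is feasibility, and the power calculation matches the test it supports. All of that stands, and is why this is offered as an improvement.

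Three limits on the gain also stand. First, its size cannot be fixed from the documents: over the range tabulated it runs from a 42% cut in variance to a 1.6% increase. Second, adjustment is not free once unequal slopes or routine HC3 standard errors are allowed for. Third, the power figures need 0.75 to be in change-SD units, and Section G2 says only that it is an effect size. In outcome-SD units with equal SDs, power goes from 80.8% to 90.0% at rho 0.5 and from 95.5% to 97.5% at rho 0.7, and is about 100% either way at rho 0.9. The variance ratios do not depend on that reading.

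A reader might infer that the change-score t-test is invalid, or that attrition biases the trial's conclusions. The documents support neither. With randomisation and complete data the change score is unbiased. Nothing in the documents says that loss depends on baseline, still less differently by arm. If it did, only the complete-case t-test would be affected: the mixed model in Section G2, fitted with group, visit and their interaction, already corrects loss that depends on baseline and arm.

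**Conclusion.** The point holds as an avoidable inefficiency with a low-cost remedy. With 44:22 completers, a common slope, equal SDs and 0.75 in change-SD units, adjusting for V1 cuts variance by about 24%, 14% or 3.5% at rho 0.5, 0.7 or 0.9, with power rising as tabulated. Under a common slope the trade is lopsided, since the most that can be lost is about 1.6% of variance. Outside that condition the loss can reach about 7-8% for slope pairs such as 0.6 in A and 1.2 in B, and routine HC3 costs about 2 power points near slope 1. It would go too far to say that adjustment always wins, or to promise a particular power. The attrition argument is a minor further reason to make the mixed model primary. The feasibility and acceptability criteria are untouched.

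**What to change.** In Section G2, name one baseline-adjusted analysis, by randomised group, as primary for each outcome.

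- Preferably use the mixed model already planned, with its fixed effects written out: V1 and V2 as responses, one common V1 mean, a group effect at V2, unstructured covariance. ANCOVA of V2 on group and V1 is the alternative.
- Define baseline A1c as the value at or before V1, because it comes from routine records and its timing is not otherwise tied to randomisation.
- Carry over the provision for unequal variances, for example by letting residual variance differ by group.
- If unequal slopes are a worry, allow a centred baseline-by-group interaction.
- Keep the change-score t-test as supportive. Leave the sample size and the stated 80% power as they are.

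The cost is plan wording and one degree of freedom, plus the precision risks set out above. No new data, visits or participants are needed.

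### Optional improvement: if changes are roughly normal but the arms' SDs differ moderately, the F pre-test under 2:1 allocation puts the primary t-test's type I error between about 4.2% and 6.1%; Welch's test throughout holds about 5.0%

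*Combined protocol and SAP*

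**What the plan says.** Section G2 (Data Analysis) states that the primary analysis of glycemic and behavioral outcomes will "compare the change in response (V1 vs. V2) between groups using an independent, two-sample t-test". It handles the variance assumption with a preliminary test: "Equal variances will be assumed, unless the F test rejects the null hypothesis of equality". It does not name the test to be used when the F test rejects, and it gives no SDs for any outcome.

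The level is general: "Statistical significance will be assessed at the 0.05 level for all hypothesis tests". Read literally, that covers the F test too. No multiplicity adjustment is made. Normality is to be checked with Q-Q plots by group, with transformation where needed, and a mixed model is planned alongside the t-test.

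Section F1 (Design) sets 2:1 randomization, 54 dyads to intervention and 28 to control. Section G2 says that a total of 82 "would be required to detect an effect size of 0.75 with 80% power", and that enrolling 82 is meant "to allow for a 20% attrition rate".

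**The concern.** When arms are equal in size, the pooled t-test tolerates unequal variances fairly well. At 2:1 it does not. The pooled variance is weighted towards the larger arm, so the standard error is too small when the smaller control arm has the larger SD, and too large in the opposite case.

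The F test is there to catch this, but with about 22 controls it has little power against moderate SD differences. When it does not reject, the pooled test is used although the SDs differ. The real level of each outcome comparison can then sit above or below the stated 0.05, and that per-test level is the only error control the plan gives for these outcomes. Because the fallback is unnamed, the primary method is also incompletely specified.

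**Working it through.** **Inputs.** From G2: two-sample t-test on change, 0.05 for all tests, effect size 0.75, 20% attrition. From F1: 54 and 28. Completers: 54 × 0.8 = 43.2 and 28 × 0.8 = 22.4, so 43 and 22. Assumed because the documents are silent: normal changes; a two-sided F test; Welch after rejection; control/intervention SD ratio *r* scanned from 0.5 to 2.

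**The plan's own figure.** The noncentrality is d × √(n₁n₂/(n₁+n₂)).

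- At 43/22: 0.75 × √(946/65) = 2.86 on 63 df, giving 80.4% power. This is the smallest 2:1 total that reaches 80%, and 65/0.8 = 81.25, rounded up to 82.
- At 54/28: 0.75 × √(1512/82) = 3.22 on 80 df, giving 88.9%.

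So 82 reproduces as the number enrolled, with 65 completers as the number analyzed.

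**Why the pooled test drifts.** Set the intervention SD to 1 and the control SD to *r*, at 43/22.

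- Squared standard error that the pooled test uses on average: [(42 + 21r²)/63] × (1/43 + 1/22)
- True variance of the difference in means: 1/43 + r²/22

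At r = 1.3 these are 1.23 × 0.0687 = 0.0845 and 0.1001. The standard error is √(0.0845/0.1001) = 0.92 of what it should be. The nominal critical value 1.998 then acts like 1.998 × 0.919 = 1.84, a two-sided level of about 7.1%. At r = 0.75 the standard error is 1.10 times too large and the level is about 3.2%.

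**What the F test recovers.** Simulated rejection rates under no treatment effect, at 43/22 (1,000,000 or more runs per point; Monte Carlo standard error at most about √(0.05 × 0.95/1,000,000) = 0.02 points near 5%):

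| Control/intervention SD ratio | F test rejects | Pooled t alone | Plan's rule | Welch throughout |
|---|---|---|---|---|
| 0.5 | 95% | 1.8% | 4.9% | 5.0% |
| 0.75 | 29% | 3.2% | 4.2% | 5.0% |
| 1.0 | 5% | 5.0% | 5.0% | 5.0% |
| 1.3 | 30% | 7.1% | 6.1% | 5.0% |
| 1.5 | 59% | 8.4% | 6.0% | 5.0% |
| 2.0 | 95% | 10.9% | 5.2% | 5.0% |

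The rule works at equal SDs and at large differences. It is more than 0.5 points from 5% only for ratios of about 0.65 to 0.9 and 1.1 to 1.75. Its extremes are about 4.2% (ratios 0.75 to 0.8) and about 6.1% (1.3 to 1.4). With all 82 analyzed (54/28) they are about 4.3% and 6.0%. Among trials in which the F test does not reject, the pooled test's error at 43/22 is about 7.4% at ratio 1.3 and 9.5% at 1.5, so a non-significant F test is little reassurance.

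**Power at effect size 0.75** (scaled by the root-mean-square SD), plan's rule v Welch:

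| Ratio | 43/22 | 54/28 |
|---|---|---|
| 0.75 | 81.4% v 83.8% | 90.0% v 91.4% |
| 1.0 | 80.4% v 79.8% | 88.8% v 88.5% |
| 1.25 | 79.2% v 76.6% | 87.7% v 86.2% |

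**Sensitivity at 43/22.**

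- F test at 0.10 instead of 0.05: the rule's range narrows to 4.4% to 5.8%.
- Heavy tails (t with 5 df): rule 4.3% to 5.7%, Welch 4.8% to 4.9%.
- Moderate skew (skewness 1), ratio 1.3: rule 5.7%, Welch 5.3%.
- Strong skew (exponential, skewness 2): rule 5.5% v Welch 5.9% at ratio 1.3, and 6.3% v 6.4% at 1.5. Here Welch is no better.

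The plan's Q-Q plot and transformation step was not simulated.

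**The case against.** The plan anticipates unequal variances and prespecifies a response that does most of the work: at a ratio of 2 it brings 10.9% down to 5.2%. What remains is about one percentage point under a condition for which the documents offer no evidence. The trial is a feasibility pilot, its feasibility and acceptability criteria rest on binomial intervals that this rule does not touch, and many outcomes are tested without adjustment, so a one-point shift per test is small beside the family-wise error already accepted. The outcomes are questionnaire scores, meter-check frequency and A1c, which may not be normal; in the non-normal cases tried at a ratio of 1.3, Welch's advantage is smaller or absent. Welch also loses power when controls are the more variable arm. The unnamed fallback could be fixed by naming it and keeping the pre-test.

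All of this is fair, and it sets the weight of the point. It does not remove it. Missing SDs argue for a test that holds its level at any ratio. Much of the power lost when controls vary more goes with the removed excess type I error. The mixed model is an additional analysis, and G2 states no arm-specific variances for it. The strong-skew limit stands and belongs with the recommendation.

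**Conclusion.** The point holds as an optional, low-cost improvement; the plan contains no error that must be corrected. For approximately normal changes at 43/22, the rule's type I error lies between about 4.2% and 6.1% depending on the SD ratio: at most about 0.8 points below and 1.1 points above the stated 0.05, and about 5% at equal or very different SDs. Welch throughout stays at about 5.0%. This rests on normal changes, a two-sided F test at 0.05, Welch after rejection, and SD ratios that are scanned because none is given. The arithmetic is secure. Whether this trial lies in the affected range is unknown.

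**What to change.** In G2, replace the sentence on the F test with:

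> Welch's unequal-variance t-test will be used for all change-score comparisons, with no preliminary variance test.

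This removes a data-dependent choice of test and names the method. It needs no extra participants or data. The cost at an effect size of 0.75, with the smaller figure for 54/28 and the larger for 43/22:

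- Equal variances: 0.3 to 0.6 power points lost.
- Control arm more variable: up to 1.5 to 2.6 points lost.
- Intervention arm more variable: up to 1.4 to 2.4 points gained.

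The Q-Q plot and transformation step should stay, because Welch brings no gain in type I error if changes remain strongly skewed.
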